## **c. Study Rationale**

The clinical benefits of Entresto are widely accepted, but there are many pathways through which these benefits may be derived. The increase in circulating natriuretic peptides are considered to decrease myocardial apoptosis and ventricular remodeling and to oppose other systemic effects of adverse activation of the renin-angiotensin and sympathetic nervous systems. The natriuretic peptides also have direct hemodynamic effects on sodium and water excretion and on vascular tone. These effects could lead to reduction in elevated pulmonary artery pressures, which are associated with many of the symptoms of HF and with the development of pulmonary hypertension which impairs right heart function and contributes to development of secondary right heart failure.

This pilot study takes advantage of the availability of the home monitoring device for HF management, and will include only patients in whom this device has already been implanted for management according to clinical indications. It will test the primary hypothesis that the

replacing ACEI/ARB therapy with Entresto will lower pulmonary artery pressure at 6 weeks compared to continuation of ACE inhibitor/ARB therapy and that that improvement will be sustained over the course of 20 additional weeks of therapy. In addition, the immediate first-dose response will be assessed on the first day of administration, with the hypothesis that the first dose will lead to immediate reduction in pulmonary artery pressures. The durability of the effect will be assessed over the next 20 weeks during the longitudinal phase, with the hypothesis that early reductions in pulmonary artery pressure will be sustained.

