### **b. Treatment Assignment and Randomization**

Randomized codes designating treatment group assignment will be generated for each patient. After informed consent is obtained, study personnel will obtain assigned to treatment group A or B based on the relevant randomization code.

Three study drugs will be utilized during the study:

Study Drug A = Masked Placebo, dosed twice daily

Study Drug B = Masked Active Entresto

Study Drug C = Masked Active Entresto

Group A will receive Study Drug A + Study Drug B for weeks 1-6, Study drug A + Study Drug C for weeks 6-12, and then open-label Entresto only for weeks 13-32.

Group B will receive Study drug A + their previous ACEi/ARB for weeks 1-6, and then, after a 2 day (minimum 36 hours as per FDA labelling) washout period, switch to Study Drug A + Study Drug C for weeks 7-12. This group will then receive open-label Entresto only for weeks 13-32 (as with Group A).

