### *Schedule of Administration*

Entresto is administered twice a day. On day 5 and day 47, patients will be instructed to hold their other morning medications and take only their first dose of Entresto and placebo or ACEi/ARB and placebo. They will then be asked to measure their PA pressures using their home CardioMEMS device 1, 2, and 3 hours after their first dose of Entresto or ACEi/ARB.

Both groups will do this on day 5 and day 47. On day 5, Group A will be measuring the first dose effect of Entresto and Group B will be measuring the first dose effect of ACEi/ARB after the washout period. On day 47, Group A will be measuring the acute effects of Entresto after 6 weeks of therapy and Group B will be measuring the first dose effects of Entresto.

Patients will also be asked to complete this “acute PA pressure measurement” schedule, i.e. holding morning medications, measuring PA pressure before and at hours 1, 2, 3 after their morning dose of Entresto or ACEi/ARB, after any dosing change.

On all other days, patients will take their morning dose of Entresto or ACEi/ARNB and placebo with their other morning medications. The evening dose of Entresto or ACEi/ARB and placebo can be taken with other evening medications as well.

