### *Other Endpoints:*

- *Death*
- *All-cause re-hospitalization*
- *Need to progress to advanced therapies (i.e. start home inotropes, place a ventricular assist device or list for cardiac transplantation)*
- *Unscheduled visits for IV loop diuretics*
- *Other interventions (i.e. nutrition referrals)*

*\*Will be 3 comparisons:*

- 1) 6 weeks of Entresto vs 6 weeks of continued ACEI/ARB (Group A compared to B at 6 weeks)
- 2) Baseline on ACEI/ARB compared to 6 weeks on Entresto (Groups A and B combined)
- 3) 12 weeks on Entresto compared to 32 weeks on Entresto in longitudinal study (all pts)

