### Secondary Endpoints:

- *Determine the mean change in PAPm in both groups on Entresto from week 12 to week 32 in longitudinal study*
  - *Statistical Plan: The changes in PAPm from week 12 to week 32 constitute continuous data. The distribution of average change in PAPm from week 8 to week 32 will be assessed in both group A and B. The distribution of changes in*

PAPm will be assessed for normality. If the distributions are normal, the results will be presented as means with standard errors. If the distributions are not normal, the results will be presented as medians with interquartile ranges.

- *Determine the difference between mean change in PAPm from baseline on ACEI/ARB to 6 weeks on Entresto (Groups A and B)*
  - Statistical Plan: The distribution of the average change in PAPm from baseline to 6 weeks will be assessed in Group A and combined with the distribution of change in PAPm from week 6 to week 12 in Group B. The combined distributions will be assessed for normality. If the combined distribution of changes in PAPm is normal, the results will be presented as means with standard errors. If the distributions are not normal, the results will be presented as medians with interquartile ranges.
  
- *Determine the impact of therapy over time on standard 6 minute walk test, assessing distance walked and changes in PAPm during recovery after the walk.*
  - Statistical Plan: These changes in distance walked from baseline to 6 weeks constitute continuous data. Therefore, the distribution of average changes in PAPm from baseline to 6 weeks will be assessed in Group A and Group B. If both distributions are normal, t-testing will be performed to compare the mean changes between groups. If the distributions are not normal, Wilcoxon testing will be used.  $P < 0.05$  will be significant.

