### **VIII. POTENTIAL BENEFITS**

#### **a. Potential Benefits to Participating Individuals**

The subjects enrolled in this study will receive Entresto at no cost. This medication decreases both HFREF mortality and hospital readmission rates.. Patients enrolled in this study will be provided with Entresto for the duration of the study (Group A 32 weeks, Group B 26 weeks). At the conclusion of the trial, subjects can discuss receiving Entresto as part of their heart failure medical therapy with their physician. It is likely that the information gained from monitoring PAP will allow earlier identification of a need for adjustment in a concomitant medication. This could lead to lower incidence of reversible side effects such as hypotension and renal dysfunction. As compensation for patient time and effort, the study will provide \$25/visit for each of the 8 required clinic visits during this study. This will cover both the cost of parking (\$10 for up to 4 hours in the BWH patient parking lot) and the cost of a meal at the hospital.

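### Comparison 3 is labelled as 12 v 32 weeks on Entresto for all patients, but Group B has about 6 and 26 weeks on drug at those visits

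*Combined protocol and SAP*

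**What the plan says.** The list of three comparisons appears twice: after the objectives (section II.a) and under Other Endpoints in Study Endpoints. It belongs to the asterisked items, and its third line reads "12 weeks on Entresto compared to 32 weeks on Entresto in longitudinal study (all pts".

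The treatment sections put the two groups on different clocks:

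- Treatment Assignment and Randomization (IV.b): "Group B will receive Study drug A + their previous ACEi/ARB for weeks 1-6". After a washout, those patients "switch to Study Drug A + Study Drug C for weeks 7-12"; Study Drug C is masked Entresto.
- Schedule of Administration (V.b): "On day 5, Group A will be measuring the first dose effect of Entresto". For day 47 it says that "Group B will be measuring the first dose effects of Entresto".
- Risks and Discomforts (VII, item a): Group B begins Entresto 6 weeks after Group A.
- Potential Benefits (VIII.a): Entresto is supplied for the length of the study, given as "Group A 32 weeks, Group B 26 weeks".

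The resting-PAPm longitudinal endpoint has no asterisk and is stated in study weeks. Its analysis text opens with "The changes in PAPm from week 12 to week 32 constitute continuous data", but the next sentence starts the interval at week 8. The longitudinal plan for NT-proBNP has the same slip: its heading subtracts week 8, and its text uses week 12.

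Study Rationale (I.c) describes durability in two ways. The primary hypothesis is a fall in PAPm at 6 weeks, and that the "improvement will be sustained over the course of 20 additional weeks of therapy". The same section then says durability will be assessed across the 20 weeks of the longitudinal phase, which the visit schedule places after the week 12 visit.

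**The concern.** Comparison 3 is written in time on drug, whereas the visits that supply its data are fixed in study time. The two scales agree, nominally, only for Group A. A report that follows the label would say that all patients were compared at 12 and 32 weeks of Entresto, when no Group B patient reaches 32 weeks.

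If the groups are pooled, the longitudinal change also averages two exposure windows that start and end 6 weeks apart. This could matter because Group B's reference visit falls about 5 to 6 weeks after its first dose. The Dose Modifications text allows increases at each clinic visit, so the response need not have levelled off by then. A continuing fall in Group B could then be read as a late effect in all patients, or a loss of effect could be diluted.

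**Working it through.** **Inputs.** First Entresto dose: day 5 in Group A and day 47 in Group B (Schedule of Administration). Planned size: 20 patients, 10 per group (Power Analysis). Longitudinal visits: study weeks 12 and 32. The documents give no visit windows, so I assume that each visit falls on day 7 × week: week 12 = day 84, week 32 = day 224.

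**The plan's own figure.** Group B starts 6 weeks later, so its total is 32 − 6 = 26 weeks. This reproduces the supply figure in VIII.a. At week 12 the nominal figure is 12 − 6 = 6 weeks.

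**Exposure at each visit** = (visit day − first-dose day) / 7:

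| Group | Study week 12 | Study week 32 | Nominal |
|---|---|---|---|
| A | (84 − 5)/7 = 11.3 wk | (224 − 5)/7 = 31.3 wk | 12 and 32 |
| B | (84 − 47)/7 = 5.3 wk | (224 − 47)/7 = 25.3 wk | 6 and 26 |

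Both windows last 20 weeks. Group B's lies 6 weeks earlier in exposure.

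**What a pooled change contains.** Write c(a–b) for the mean change between a and b nominal weeks on drug. Assume equal groups with the same mean course by time on drug.

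- Group A: c(12–26) + c(26–32)
- Group B: c(6–12) + c(12–26)
- Pooled: ½c(6–12) + c(12–26) + ½c(26–32)

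The label describes c(12–26) + c(26–32) for everyone. Pooled minus labelled is therefore ½[c(6–12) − c(26–32)]. This is zero if the response is stable in both periods, or changes equally in both.

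**Illustration only.** The documents give no time course. Suppose that PAPm falls by 5 mm Hg in all (20% of 25, from Power Analysis) and approaches that level exponentially. The time constants are my assumption. Using the exposures in the table, the week 12 to 32 change in mm Hg would be:

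| Time constant | Group A | Group B | Pooled | Pooled − A |
|---|---|---|---|---|
| 2 wk | −0.02 | −0.36 | −0.19 | −0.17 |
| 4 wk | −0.30 | −1.32 | −0.81 | −0.51 |
| 6 wk | −0.74 | −2.00 | −1.37 | −0.63 |
| 8 wk | −1.12 | −2.37 | −1.75 | −0.63 |

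The distortion ranges from slight to modest, depending wholly on a speed of response that the plan does not give.

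**Aligned windows.** Group A, study weeks 6 to 26: 42 − 5 = 37 to 182 − 5 = 177 days on drug. Group B, study weeks 12 to 32: 84 − 47 = 37 to 224 − 47 = 177 days. The two match under the visit-day assumption, and only approximately in practice.

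**The week 8 reference.** At study week 8 Group B has (56 − 47)/7 = 1.3 weeks of Entresto, so which reference week applies makes a real difference.

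**The case against.** The strongest reply is that the fault is one of labelling in a secondary, descriptive analysis of a pilot. The physical and mental stress tests are defined operationally as week 32 minus week 12, the staggered start is disclosed in several sections, both windows last 20 weeks, and neither co-primary endpoint is touched. All of that stands, and it limits the point without removing it: the label is still untrue for Group B.

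A reader might infer four stronger things that the documents do not support.

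- *That the resting-PAPm endpoint is mislabelled.* It carries no asterisk and is stated in study weeks, so it makes no claim about time on drug.
- *That PAPm is certainly pooled over weeks 12 to 32.* The text says that the change is assessed in both groups, which may mean group by group. The next PAPm item speaks explicitly of combining distributions, and the longitudinal plans do so only for the exploratory KCCQ items. The words in comparison 3 about all patients point to pooling, but only for the starred endpoints.
- *That the stated durability hypothesis goes untested in Group A.* On one reading of Study Rationale (6 weeks plus 20), Group A's change between weeks 6 and 12 lies outside both planned PAPm windows. But the same section places durability in the longitudinal phase, which is weeks 12 to 32. The two statements need reconciling; neither can be taken alone as the hypothesis.
- *That the week 12 to 32 PAPm endpoint should be replaced by an aligned one.* Group A's weeks 6 to 26 would include masked treatment with two-weekly visits, while Group B's weeks 12 to 32 are essentially open-label with sparser visits. Replacement would also discard Group A's data after week 26, the longest exposure in the trial. Alignment is therefore useful as an addition.

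**Conclusion.** Wrong as written. Comparison 3 assigns 12 and 32 weeks of Entresto to all patients. On the plan's own dates and supply figures, half of them (10 of 20) have nominally 6 and 26. The nominal finding does not depend on how visit days are counted; the 5.3 and 25.3 week figures do.

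Any pooled week 12 to 32 result mixes exposure windows of about 12–32 and 6–26 weeks, and this applies to resting PAPm as well if it is pooled. Against the labelled quantity the distortion is half the difference between the 6–12 week change and the 26–32 week change on drug, given equal groups and a common time course. The documents do not allow its size to be estimated, so no material bias is shown. The correction is still worth making, because the durability result would otherwise be reported at an exposure that Group B never had.

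**What to change.** 1. In both places, relabel comparison 3 as study week 12 to study week 32 (about 12 to 32 weeks on Entresto in Group A, about 6 to 26 in Group B).
2. Report every longitudinal result by group as well as pooled.
3. Keep the PAPm week 12 to 32 endpoint. Add a supportive PAPm analysis aligned on first Entresto dose, using daily home readings from about study weeks 6 to 26 in Group A and 12 to 32 in Group B. Give the mean change with a 95% confidence interval, and note that masking and visit frequency differ between the two windows. The clinic tests and NT-proBNP have no week 26 visit, so for them items 1 and 2 suffice.
4. Reconcile the week 8 references with week 12 in the PAPm and NT-proBNP longitudinal plans, and the two durability statements in Study Rationale.

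The cost is wording and a little extra analysis. Home pressures are transmitted every morning and remain retrievable, so no visit or measurement is added.

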## Statistical Analysis

### Co-Primary Endpoints:

#### *Intensive Phase:*

- *Determine the difference between mean change in mean pulmonary artery pressure (PAPm) after 6 weeks on Entresto compared to 6 weeks on continued ACEi/ARB*
  - *Statistical Plan: These changes from baseline to 6 weeks constitute continuous data. Therefore, the distribution of average changes in PAPm from baseline to 6 weeks will be assessed in Group A and Group B. If both distributions are normal, t-testing will be performed to compare the mean changes between groups. If the distributions are not normal, Wilcoxon testing will be used. P <0.05 will be significant.*

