## III. PATIENT POPULATION

### a. Inclusion/Exclusion Criteria

#### *Inclusion Criteria*

Key inclusion criteria: The disease to be studied is HF with reduced ejection fraction (HFrEF).

1. Patients able to provide written informed consent
2. Patients  $\geq 18$  years of age, male or female, in NYHA Class II- III HF, previously hospitalized for HFrEF with LVEF  $< 35\%$  (measured within the past year), and who have no subsequent LVEF  $> 35\%$ .
3. Systolic BP  $\geq 95$  mm Hg at most recent clinical assessment.
4. Stable, ambulatory patients without the need for change in diuretics and other HF drugs (RAS blockers, beta blockers or mineralocorticoid receptor blockers) during the past 5 days
5. Currently treated with an ACEi or ARB
6. CardioMEMS HF System implanted for NYHA Class III HF. Patient transmitting information regularly and system functioning appropriately.
7. NT-proBNP  $> 500$  pg/ml within 90 days of CardioMEMS implantation.
8. Average PAPm  $> 20$  mm Hg during the 7 days prior to enrollment, including at least 4 daily measurements.

Women of childbearing age must be practicing a highly effective method of contraception. Acceptable methods of “high effective contraception” include abstinence, prior sterilization, contraceptive implants, intrauterine device, injectable contraception, contraception pills, contraception patches, and contraceptive rings.

*Exclusion Criteria*

1. Treatment with vasodilators (other than nitrates, hydralazine) and/or IV inotropic drugs.
2. Entresto taken within the past 30 days.
3. History of hypersensitivity, intolerance or angioedema to previous renin-angiotensin system (RAS) blocker, ACE inhibitor, ARB, or Entresto.
4. eGFR < 30 ml/min/1.73 m^2 as measured by the simplified MDRD formula.
5. Serum potassium > 5.5 mmol/L.
6. Acute coronary syndrome, stroke, transient ischemic attack, cardiovascular surgery, PCI, or carotid angioplasty within the preceding 3 months.
7. Coronary or carotid artery disease likely to require surgical or percutaneous intervention within 3 months after trial entry.
8. Non-cardiac condition(s) as the primary cause of dyspnea.
9. Implantation of a cardiac resynchronization therapy device (CRT/D) within the preceding 3 months or intent to implant a CRT/D, which may alter the pressures during the course of the study.

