#### **e. Data to be Collected**

##### **Baseline Clinic Visit, Variables to be Collected:**

- **Demographics and HF History (first visit only)**
  - Age
  - Sex (male/female)
  - Race (white, black, other)

- Ethnicity (Hispanic, non-Hispanic)
- Type of Insurance (Medicare, Medicaid, commercial, other)
- Etiology of heart failure (ischemic, nonischemic)
- NYHA (I-IV) in clinic
- Number of previous hospitalizations for heart failure in the past year
- Time since diagnosis of heart failure (years)
- Time since placement of CardioMEMS (months)
- Time of most recent echo (< 1 month, 1-5 months, 6-12 months, > 1 year)
  - LVEF
  - LVDD mm
  - MR (0,trace,mild/mod/mod-sev/severe)
  - TR (0,trace,mild/mod/mod-sev/severe)
- **Medication Data**
  - Beta blocker total daily dose (metoprolol equivalents, mg/d), has there been a dose change
  - ACEi no/yes (if yes, total daily dose in captopril equivalents, mg/d), has there been a dose change
  - ARB no/yes (if yes, total daily dose in valsartan equivalents, mg/d), has there been a dose change
  - Nitrate no/yes (if yes total daily dose mg), has there been a dose change
  - Hydralazine no/yes (if yes total daily dose mg), has there been a dose change
  - Diuretic total daily dose (furosemide equivalents, mg/d), has there been a dose change
  - Use of thiazide diuretic in past 14 days (no/yes) if yes, # days, has there been a dose change
- **Clinical Assessment**
  - History:
    - Orthopnea or paroxysmal nocturnal dyspnea within last 14 days (no/yes) If yes, # days
    - Bendopnea within last 14 days (no/yes) If yes, # days
    - Dizziness or lightheadedness on standing (no/yes)
      - If yes, rare / 1-2 x weekly / only if stand quickly / often
    - Symptoms limiting bathing and dressing (no/yes) If yes, #days
  - Examination
    - HR sitting
    - Rhythm (from EKG) regular (SR/paced/
    - SBP/ DBP mmHg sitting and standing
    - Jugular venous pressure (estimated cmH20)
    - S3 yes/ no

- Systolic murmur (0,1,2,3,4)
  - Rales (absent/bases/one-quarter/one third up)
  - Hepatomegaly no/yes if yes, 1-3, 4-6, > 6 cm)
  - Peripheral edema (none/trace/1+/2+/3+/4+)
- **PA pressure measurements baseline in clinic (recorded by staff)**
  - PA systolic/ diastolic/ mean pressures at rest (in clinic, mmHg)
- **Planned Medication Changes after this Visit**
  - Do you plan to uptitrate Entresto or ACEi/ARB?
  - If not, why not? (postural hypotension, resting hypotension, renal dysfunction, fatigue)

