## Power Analysis

There will be 20 patients total, 10 in each group.

*Between group comparison:* This sample size will provide 90% power with 2-sided alpha of 0.05 to detect a 20% difference between the 2 groups (Entresto and ACEI/ARB) in the PAPm change at 6 weeks, based on an assumed baseline PAPm of 25 mm, using a t-test with a standard deviation in the mean change of as high as 3.4. We do not yet have data on which to estimate the standard deviation of this change, but we have found a standard deviation of 3-4 mm Hg of PAPm pressures during 5 day periods in stable patients followed on Cardiomems devices at Brigham and Women's Hospital (unpublished data).

*All patients after 6 weeks of Entresto compared to chronic ACEI/ARB at baseline:* There is additional power for this highest secondary endpoint. Assuming the PAPm baseline on ACEI/ARB mean of 25mm, a sample size of 20 patients will provide 90% power with two-sided alpha of 0.05 paired t-test to detect a 20% decrease (to PAPm of 20 mm) after 6 weeks of Entresto, with a standard deviation for the change as high as 6.8.

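### The 90% power stated for the 6-week comparison is 87.5% for the t-test it names; separately, one prespecified ANCOVA on a named PAPm value is a cheap improvement on the normality-gated test

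*Combined protocol and SAP*

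**What the plan says.** **Power.** The Power Analysis section fixes the size: "There will be 20 patients total, 10 in each group". It claims 90% power at two-sided 0.05 for a 20% between-group difference in PAPm change, taking a baseline of 25 mm Hg and "using a t-test with a standard deviation in the mean change of as high as 3.4". On that SD it adds "We do not yet have data on which to estimate the standard deviation of this change", and offers instead "we have found a standard deviation of 3-4 mm Hg of PAPm pressures during 5 day periods in stable patients".

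**Analysis.** Under Statistical Analysis, Co-Primary Endpoints, Intensive Phase, "the distribution of average changes in PAPm from baseline to 6 weeks will be assessed in Group A and Group B". If both are normal, "t-testing will be performed to compare the mean changes between groups. If the distributions are not normal, Wilcoxon testing will be used". Significance is at 0.05. Baseline enters only by subtraction. The section gives no normality test or cut-off and no confidence interval.

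**Which PAPm.** Neither this section nor the endpoint lists say which readings are averaged. Inclusion criterion 8 defines a home average "during the 7 days prior to enrollment, including at least 4 daily measurements", but for eligibility only. Section V.e also collects resting clinic readings and daily home transmissions, of which the Monday and Thursday values are routinely entered on the case report form. It says that all transmitted readings stay retrievable from the device website.

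**The concern.** The first matter is a stated property that the design does not have: the power claim names the t-test, but the figure comes from a normal approximation that ignores estimation of the variance on 18 degrees of freedom.

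The second is a choice of analysis that could be better. The objective is a difference in mean change, but if the rule selects Wilcoxon the result is a rank comparison that does not estimate that difference. Subtracting baseline leaves chance baseline imbalance unadjusted whenever the slope of week-6 on baseline PAPm is not 1, and no stratification by baseline PAPm is described. With arms of 10, the noise in the PAPm value also depends heavily on how many readings are averaged, which the plan leaves open.

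**Working it through.** **Inputs from the Power Analysis section.** n = 10 per arm; difference 0.20 × 25 = 5 mm Hg; SD of change 3.4; two-sided alpha 0.05.

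**1. The plan's figure.** Standard error = 3.4 × √(2/10) = 1.521, so 5/1.521 = 3.288. Normal approximation: Φ(3.288 − 1.960) = 90.8%. The largest SD giving 90% this way is 3.45, consistent with the plan's limit of 3.4.

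**2. The exact t-test.** Noncentral t, 18 df, critical value 2.101, noncentrality 3.288: power 87.5%. Exact 90% requires an SD of at most 3.26 at 10 per arm. For reference, 11 per arm at SD 3.4 gives 90.6%.

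**3. ANCOVA, equal variances.** The relation between baseline and week-6 PAPm is not in the documents, so it is assumed and shown as a range. Residual SD = 3.4 × √((1 + ρ)/2). Power is from the noncentral t with 17 df, averaged over chance baseline imbalance.

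| Assumed correlation ρ | Residual SD | Power |
|---|---|---|
| 0.5 | 2.94 | 93.4% |
| 0.7 | 3.13 | 90.3% |
| 0.8 | 3.23 | 88.6% |
| 0.9 | 3.31 | 86.9% |
| slope 1 | 3.40 | 85.2% |

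Break-even with the t-test is at a residual SD of about 3.29 (ρ about 0.87).

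**4. ANCOVA, respecting the entry rule.** Inclusion criterion 8 requires PAPm above 20 mm Hg, which narrows baseline. Assume a bivariate normal with equal variances before selection, cut at 20, with mean 25 after selection and SD of change 3.4. Residual SD = √(3.4² − (1 − slope)² × SD_base²).

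| SD before selection | Baseline SD after | Slope | Residual SD | Power | Against 87.5% |
|---|---|---|---|---|---|
| 4 | 3.13 | 0.61 | 3.17 | 89.6% | +2.1 |
| 5 | 3.47 | 0.75 | 3.29 | 87.4% | −0.1 |
| 6 | 3.72 | 0.83 | 3.34 | 86.4% | −1.1 |
| 8 | 4.07 | 0.91 | 3.38 | 85.7% | −1.8 |

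**5. Effect of the normality gate.** Simulation of 20,000 trials with normal data, assuming Shapiro-Wilk at 5% in each arm and Wilcoxon if either arm fails. The gated verdict differs from a fixed t-test in 0.6% of trials at 5 mm Hg and 0.9% at 3.5 mm Hg. Under the null the gated rule rejects in 5.1%. With exponential or t(3) data its type I error stayed close to 5% (5.3% and 4.7%).

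**6. Non-normal residuals.** Simulation of 6,000 trials, baseline SD 4, gated rule against ANCOVA:

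| Residuals | Slope 0.6 | Slope 0.75 | Slope 0.9 |
|---|---|---|---|
| Exponential | 90.7% v 90.7% | 91.2% v 87.0% | 90.8% v 84.9% |
| t(3) | 92.9% v 92.4% | 94.1% v 90.3% | 94.2% v 88.4% |

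**7. Averaging.** If the quoted 3-4 mm Hg is within-patient and readings are independent (both assumed), noise alone gives an SD of change of √(2/k) × 3 to √(2/k) × 4 for k readings at each end: 4.2 to 5.7 for k = 1, 2.1 to 2.8 for k = 4, and 1.6 to 2.1 for k = 7. Correlated days would give less benefit.

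**The case against.** The strongest reply is that nothing here is an error of inference. The change-score comparison is unbiased, the gated rule holds its level, and this is a pilot. That stands.

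Four stronger readings are tempting, and the documents do not support them.

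- **That the gate makes the result unstable.** A t-test and a Wilcoxon test run on the same data disagree at 0.05 in about 5% of trials at 5 mm Hg and 8% at 3.5 mm Hg. But the plan does not run both every time; it switches only when the check fails. The relevant figure is the 0.6% to 0.9% in step 5. A discretionary check could do somewhat worse, but even choosing the better p-value gave a type I error of only 5.5% to 5.8%.
- **That one normal and one non-normal arm is left undecided.** In such arms exactly one fails in about 10% of trials. But the t-test is conditional on both arms being normal, so the ordinary reading sends this case to Wilcoxon.
- **That ANCOVA restores the 90%.** The equal-variance figures that suggest so imply a baseline SD of 3.4 to 7.6 for ρ of 0.5 to 0.9. In an untruncated normal with mean 25, that puts 7% to 26% of patients below 20 mm Hg, whom the entry rule excludes. With the rule respected the gain is about zero on average. Averaging over 7 days also raises the slope, which shrinks any gain.
- **That power is really 46% to 70%.** The t-test has that power at an SD of change of 5.7 to 4.2, which is single-reading noise at each end. It needs three assumptions: within-patient SD, independent readings, and one reading at each end. The Power Analysis section does not state the first, and the plan's reference to average changes may point away from the third.

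It is also fair to say that 2.5 points of power is small beside an SD that the plan admits has no data behind it. That limits the importance of the restatement, but the stated figure is still wrong for the named test.

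**Conclusion.** Two conclusions hold.

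First, the 90% is a normal-approximation figure. For the t-test named, at 10 per arm, 5 mm Hg and SD 3.4, power is 87.5%, or 90% if the SD is at most about 3.26. This rests only on the plan's own inputs, reading 20% of 25 as 5 mm Hg. It does not show that the trial needs more patients.

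Second, one baseline-adjusted model on named PAPm values would be a modest improvement over the gated rule. The benefit is a single estimate that matches the stated difference in means, allowance for chance baseline imbalance, and less noise from multi-day averages. A power gain is not part of the case. Under normal residuals ANCOVA runs from 93.4% (ρ = 0.5, equal variances) to 85.2% (slope 1), and about +2 to −2 points against the t-test under the entry rule. These ranges rest on an assumed baseline/week-6 relation, and the gate figures on an assumed Shapiro-Wilk check.

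**What to change.** **Power Analysis section.** Restate the between-group power as 87.5% at SD 3.4, or as 90% at SD up to about 3.26. Enrolment stays as planned, and ANCOVA should not be credited with making up the difference.

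**Co-primary 6-week analysis.** Replace the gated rule with one prespecified ANCOVA of week-6 PAPm on randomised group and baseline PAPm. Form both values the same way from home readings, for example 7-day averages with a minimum of four readings, before enrolment and before the week-6 visit. Report the adjusted mean difference with a 95% CI, and a rank-based or permutation sensitivity analysis.

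**Cost.** SAP wording, plus retrieval of home readings in two 7-day windows; no new measurement or visit. The statistical price is one degree of freedom (17 rather than 18), up to about 2 points of power if the slope is near 1, and about 4 to 6 points against the gated rule if residuals are clearly non-normal and the slope is 0.75 to 0.9. The sensitivity analysis is there for that last case.

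**If ANCOVA is declined.** Name the same two PAPm values and fix one test of the mean change with a CI.
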